## 3. STUDY DESIGN

### 3.1. GENERAL DESCRIPTION

This is an open-label, single-arm, multi-center study to assess the contraceptive efficacy and safety of the NOMAC-E2 COC in postmenarcheal premenopausal women aged 14 to 35 years (inclusive) at the time of study entry.

The total duration of study participation will be up to 60 weeks, which includes a Pre-treatment Period of maximally 6 weeks, a Treatment Period of 52 weeks, and a Follow-up Period of 2 weeks after the last intake of study treatment. Schedule of activities can be found in Section 1.3 of the protocol.

All participants will receive NOMAC-E2 COC. Participants will take one tablet of study treatment per day for thirteen 28-day treatment cycles. The NOMAC-E2 COC active tablets contain 2.5 mg NOMAC and 1.5 mg E2 and will be used in a 24/4 regimen, i.e., 28-day cycles with 24 days of active tablet intake followed by 4 days of placebo tablet intake.

---

Document: [REDACTED]

Author: [REDACTED]

Version Number:

2.0

Version Date:

23APR2024

[figure not shown]
Template No.: CS\_TP\_BS016 Revision 6

Reference: CS\_WI\_BS005

Effective Date: 02Dec2019

Copyright © 2009, 2010, 2012, 2016, 2018, 2019 [REDACTED]. All rights reserved. The contents of this document are confidential and proprietary to [REDACTED] and its subsidiaries. Unauthorized use, disclosure or reproduction is strictly prohibited.

### Study Schema

Abbreviation: EOS=End of Study; ET=Early Termination; Max=maximum.

\* Time between Visit 2 and Day 1 will depend on the onset of menstruation or the completion of the pre-study contraceptive.

### 3.2. CHANGES TO ANALYSIS FROM PROTOCOL

Only safety analyses will be performed for this study. Efficacy and PK analyses will not be performed.

Consequently, the Safety Analysis Set (SAF), Allocated Participants Set (APS), and Multiple Enrollment Set (MES) as described in [Section 5](#) will be used.

The protocol (footnote to Table 11) specifies that laboratory and vital will be analysed up 28 days after last tablet intake; however, the protocol also specifies that the follow-up visit occurs 14 days (+5 days) after the last tablet. Therefore, this is now corrected in the footnote of Table B of the SAP.

### 4. PLANNED ANALYSES

Only a final analysis will be performed for this study. No interim analysis is planned.

#### 4.1. DATA MONITORING COMMITTEE

There was no data monitoring committee for this study.

Document:

Version Number:

2.0

Version Date:

23APR2024

Template No.: CS\_TP\_BS016 Revision 6

Reference: CS\_WI\_BS005

Effective Date: 02Dec2019

Copyright © 2009, 2010, 2012, 2016, 2018, 2019 [REDACTED]. All rights reserved. The contents of this document are confidential and proprietary to [REDACTED] and its subsidiaries. Unauthorized use, disclosure or reproduction is strictly prohibited.

## 4.2. FINAL ANALYSIS

All final, planned analyses identified in this SAP will be performed by [REDACTED] Biostatistics following sponsor authorization of this SAP, analysis set determination, and database lock.

## 5. ANALYSIS SETS

Agreement and authorization of participants included/excluded from each participant-level analysis set will be conducted prior to database lock.

The all participants enrolled (ENR) set will include all participants who provided informed consent for this study and were entered in IRT correctly.

Allocated Participants Set (APS) will include all participants who were allocated to treatment regardless of if any dose was taken.

Safety Analysis Set (SAF) will include all participants allocated to treatment who took at least one dose of study treatment, as determined based on the Drug Accountability eCRF (i.e., participants are expected to either have a date of first dose or indicate that no study drug has been taken). The SAF population will be used for the analysis of all safety data in this study.

If some participants were enrolled in the study more than once, these participants will be excluded from all analysis sets mentioned above (except in pregnancies listing and AE listing).

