9.3.5 Safety Analysis Population

The All-Participants-as-Treated (APaT) population will consist of all participants allocated to treatment who took at least one dose of study treatment.

The APaT population will be used for the analysis of all safety data in this study.

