9.4 Statistical Analyses

The SAP will be finalized prior to database lock and it will include a more technical and detailed description of the statistical analyses described in this section. The SAP document will provide further details regarding the definition of analysis variables and analysis methodology to address all study objectives. The SAP will serve as a complement to the protocol and will supersede the protocol in case of differences.

Statistical analysis will be performed using SAS® software (version 9.4 or higher) (SAS Institute Inc., Cary, NC, USA).

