## 6.3. DERIVED TIMEPOINTS

The ‘Last measurement’ is defined as the last value obtained during the study.

Assessments collected at protocol visit V7 or ET will be displayed in listings as V7 for participants who started Cycle 13 and as ET for those who did not.

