## 8. OUTPUT PRESENTATIONS

Conventions for presentation of data in outputs will be included in the Programming Conventions for Outputs document.

The templates provided with this SAP describe the presentations for this study and therefore the format and content of the summary tables, figures, and listings to be provided by [REDACTED] Biostatistics.

All data will be listed, and summary tables will be provided. Continuous variables will be summarized for the measured values and change from baseline values using the number of observations, mean, standard deviation, median, minimum, and maximum. Categorical variables will be summarized with counts and percentages for each category.

---

Document: [REDACTED]

Author: [REDACTED]

Version Number:

2.0

Version Date:

23APR2024

Template No.: CS\_TP\_BS016 Revision 6

Reference: CS\_WI\_BS005

Effective Date: 02Dec2019

Copyright © 2009, 2010, 2012, 2016, 2018, 2019 [REDACTED]. All rights reserved. The contents of this document are confidential and proprietary to [REDACTED] and its subsidiaries. Unauthorized use, disclosure or reproduction is strictly prohibited.

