### **15.3. LABORATORY EVALUATIONS**

Results from the central laboratory will be included in the reporting of this study for hematology, biochemistry, and urinalysis. A list of laboratory assessments to be included in the outputs is included in Appendix 3 of the protocol (Table 10). For each parameter, normal reference ranges and safety ranges will be presented.

Presentations will use International System of Units (SI). Results will be converted as needed prior to the analysis. Quantitative laboratory measurements reported as '< X', i.e., below the lower limit of quantification (LLQ), or '> X', i.e., above the upper limit of quantification (ULQ), will be converted to X for the purpose of quantitative summaries, but will be presented as recorded, i.e., as '< X' or '> X' in the listings.

Document:

Version Number:

2.0

Version Date:

23APR2024

Template No.: CS\_TP\_BS016 Revision 6

Reference: CS\_WI\_BS005

Effective Date: 02Dec2019

Copyright © 2009, 2010, 2012, 2016, 2018, 2019 [REDACTED]. All rights reserved. The contents of this document are confidential and proprietary to [REDACTED]. Unauthorized use, disclosure or reproduction is strictly prohibited.

Actual and change from baseline in laboratory test values will be summarized by visit (including Baseline and last measurement) under each of hematology, biochemistry, and urinalysis. All available lab data will be included in the data listings.

In addition, markedly abnormal liver function-related laboratory tests will be summarized during all visits in the study based on the criteria listed below in Table C.

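### SAP 5 takes treated participants who enrolled more than once out of the safety set, a departure from the protocol's APaT population that SAP 3.2 neither states nor justifies

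*SAP*

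**What the plan says.** Protocol 9.3.5 sets the safety population: "The All-Participants-as-Treated (APaT) population will consist of all participants allocated to treatment who took at least one dose of study treatment". It is to be used for all safety data and carries no condition on the number of enrolments. Protocol 9.4 adds: "The SAP will serve as a complement to the protocol and will supersede the protocol in case of differences".

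SAP 5 defines three sets: ENR (consented and correctly entered in IRT), APS (allocated, dosed or not) and SAF. For the last it says: "Safety Analysis Set (SAF) will include all participants allocated to treatment who took at least one dose of study treatment". The section then closes with an exception for anyone enrolled in the study more than once: "these participants will be excluded from all analysis sets mentioned above (except in pregnancies listing and AE listing". SAP 15.1 and 15.6 repeat the two listing exceptions.

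SAP 3.2, the section for changes from protocol, reads: "Consequently, the Safety Analysis Set (SAF), Allocated Participants Set (APS), and Multiple Enrollment Set (MES) as described in" Section 5 will be used. It does not mention the exclusion or give a reason, and Section 5 as shown contains no definition of the MES.

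SAP 15 bases all safety outputs on the SAF. SAP 9 undertakes to account for everyone who consented. SAP 9.1 shows reasons for exclusion from each set on ENR, and SAP 9.2 summarizes major and critical deviations on the SAF.

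**The concern.** The study stopped early and the SAP limits the report to safety. The usual rule for a safety set is that exposure decides membership: a woman who took the drug is counted. Here an administrative fact, a second enrolment, overrides exposure. A treated woman who enrolled twice would leave the tables of treatment-emergent, serious and clinical-interest events, discontinuations, laboratory values, exposure, compliance and overdose.

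The exclusion is also hard to see from the planned outputs. The display of exclusion reasons is built on ENR, and the deviation summary on the SAF. The same women have been taken out of both. A reader of the tables could take them to cover every treated participant.

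At stake is mainly a rare serious event or event of clinical interest in one of these women. It would appear in a listing while the summary table shows no case.

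**Working it through.** No sample size, power or published figure rests on this rule, so there is no plan figure to reproduce. The check has two parts.

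**Comparing the texts**

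1. Membership: protocol 9.3.5 asks for allocation plus one dose. SAP 5 asks for allocation plus one dose and, through its closing sentence, no second enrolment. The SAF is therefore APaT minus the treated multiple enrollers.
2. Status: protocol 9.4 lets the SAP prevail, so the narrower set is the operative one.
3. Declaration: SAP 3.2 goes as far as correcting a table footnote, but on this point gives only a set name and a cross-reference. The exclusion itself is written in Section 5; the reason and the MES definition are in neither place.
4. Visibility: the closing sentence of SAP 5 also covers ENR. The ENR-based display of exclusion reasons (SAP 9.1) would then omit the women it should explain, in tension with SAP 9.

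**Size, under stated assumptions**

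Let N be the number treated and k the treated multiple enrollers. Neither is given. I assume k = 10 and N = 300 or 1,000, and also N = 1,878, the planned allocation, which the stopped study need not have reached. If k = 0 nothing changes.

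*Common event.* If the rate is 50% in the other women and r in the excluded women, leaving them out moves the percentage by (k/N) × (r − 0.50). With r = 60%:
- N = 300: 10/300 × 0.10 = 0.33 points
- N = 1,000: 10/1,000 × 0.10 = 0.10 points
- N = 1,878: 10/1,878 × 0.10 = 0.05 points

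With r at 0% or 100% the bounds are 1.7, 0.5 and 0.3 points.

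*Rare event with one case among all treated women.* If each woman is equally likely to be the case, the chance that it falls among the excluded is k/N. When it does, the table reads 0/(N − k) instead of 1/N. The Clopper-Pearson 95% upper limit is 1 − 0.025^(1/n) for 0 of n, and the 97.5th percentile of Beta(2, N − 1) for 1 of N.

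| N | k/N | All treated: 1/N (upper limit) | As written: 0/(N − k) (upper limit) |
|---|---|---|---|
| 300 | 3.3% | 1/300 = 0.33% (1.84%) | 0/290 = 0% (1.26%) |
| 1,000 | 1.0% | 1/1,000 = 0.10% (0.56%) | 0/990 = 0% (0.37%) |
| 1,878 | 0.5% | 1/1,878 = 0.05% (0.30%) | 0/1,868 = 0% (0.20%) |

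With k = 40 of 1,878 the chance is 2.1%. With three cases and k = 10, the chance that at least one is missing is 1 − C(N − 10, 3)/C(N, 3), which gives 9.7%, 3.0% and 1.6%.

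The interval columns apply only if intervals are produced. Protocol 9.4.3 plans them for events of clinical interest. SAP 15.1.5 and SAP 8 do not repeat that.

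**The case against.** A reader might infer that SAP 5 contradicts its own SAF definition. It does not: a general definition is followed by an express exception, and the protocol allows the SAP to prevail. The difference is from the protocol, and the defects are the undeclared reason and the unfinished MES.

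The exception also has a plausible motive. Protocol 8.1.4 allows one treatment number per participant, so a second treated enrolment is a breach that makes Day 1, baseline, exposure and compliance ambiguous. Even the last measurement, which SAP 6.3 says "is defined as the last value obtained during the study", could come from the later enrolment. Set membership is to be agreed before database lock, and the report is descriptive, with no tests. This explains why a rule is needed, but it does not require removing treated women from the tables.

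A reader might also infer that the safety data of these women disappear. The documents do not support that. Their adverse events and pregnancies are listed by name of the group, and general statements point the same way: "All data will be listed, and summary tables will be provided" and, for laboratory results, "All available lab data will be included in the data listings". The output templates are not visible, and one may tabulate the MES or show the exclusions.

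Two further readings go too far. One is that the report will print a zero for an event of clinical interest that did occur: the instruction to summarize these events even at zero incidence is in protocol 9.4.3, and SAP 15.1.5 plans only a summary by system organ class and preferred term. The other is that properly rescreened women will be dropped. Protocol 5.4 and 8.1.3 keep them under one screening number, and nothing equates a repeat consent with a second enrolment. What stands is that the SAP never defines the term.

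**Conclusion.** The point holds as a departure from the protocol's safety population that is inadequately declared and should be fixed before the tables are final. As written, treated multiple enrollers leave all SAF-based safety summaries and leave ENR. SAP 3.2 gives no reason, and the set that might hold them is named but not defined in Section 5 as shown.

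The wording is certain; the consequence is not. The number of women is not given and may be zero. For an assumed 10 women, a common event moves by about 0.05 to 0.33 points in the illustration, and a lone rare case drops out of the table with a chance of 0.5% to 3.3%, while remaining in the listing. The argument for changing the rule is that safety is all this report offers and that the change is cheap, not that a large bias has been shown.

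**What to change.** - **SAF:** keep each treated woman once. Use her first treated enrolment for Day 1, baseline, visit windows, exposure, compliance, last measurement and the treatment-emergent window, so that events and exposure cover the same period.
- **MES:** define it in Section 5 and give it one table of exposure and adverse events from later enrolments. Flag there any serious event or event of clinical interest from a later enrolment, with a footnote in the main table.
- **ENR and APS:** count each woman once, and report the number of multiple enrollers in disposition.
- **Sensitivity:** give the treatment-emergent overview with and without these women.
- **Definition:** say what enrolled more than once means, and that permitted rescreening under the same screening number does not count.
- **SAP 3.2:** record any departure from APaT that remains, with its reason.

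Two simpler-looking options are worse. Merging enrolments counts the gap as treatment: with an illustrative 84 days on drug, 60 off and 84 on, exposure would read 228 days against 168 actually on drug (+36%), and perfect intake would show as 168/228 = 73.7% compliance. Counting events from every enrolment in the main table lengthens the period at risk for these women and so raises their chance of at least one event, which affects participant-based percentages.

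The cost is SAP wording, a rule linking a woman's records, one MES table and one extra overview. The downside is that events from later enrolments appear in the MES table and not in the main percentages, which is why the footnote is needed. If no treated woman enrolled twice, only the wording changes.

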## 6. GENERAL CONSIDERATIONS

### 6.1. REFERENCE START DATE AND STUDY DAY

Study Day will be calculated from the reference start date and event start date and will be used to show number of days since start/stop day of assessments and events relative to first dose of study treatment.

---

Document: [REDACTED]

Author: [REDACTED]

Version Number:

2.0

Version Date:

23APR2024

Template No.: CS\_TP\_BS016 Revision 6

Reference: CS\_WI\_BS005

Effective Date: 02Dec2019

Copyright © 2009, 2010, 2012, 2016, 2018, 2019 [REDACTED] All rights reserved. The contents of this document are confidential and proprietary to [REDACTED] and its subsidiaries. Unauthorized use, disclosure or reproduction is strictly prohibited.

Reference start date (Day 1) is defined as the day of the first dose of study treatment.

If the date of an event is on or after the reference date, the following will be calculated:

Study Day = (date of event – reference date) + 1.

If the date of the event is prior to the reference date, then:

Study Day = (date of event – reference date).

## 6.2. BASELINE

Unless otherwise specified, baseline is defined as the last non-missing measurement taken prior to reference start date (including unscheduled assessments). In the case where the last non-missing measurement and the reference start date coincide, that measurement will be considered pre-baseline with the following exceptions:

Adverse events (AEs) and medications commencing on the reference start date will be considered as either pre-baseline or post-baseline based on the collected eCRF assessment of whether the item started prior to the start of study treatment.

## 6.3. DERIVED TIMEPOINTS

The ‘Last measurement’ is defined as the last value obtained during the study.

Assessments collected at protocol visit V7 or ET will be displayed in listings as V7 for participants who started Cycle 13 and as ET for those who did not.

## 6.4. RETESTS, UNSCHEDULED VISITS AND EARLY TERMINATION DATA

In general, for by-visit summaries, data will be presented following the mapping described in Table B (section 6.5 of this SAP), including scheduled and unscheduled measurements, however only scheduled time points will be summarized. Additionally, unscheduled measurements will contribute to the ‘Last measurement’ value (defined in section 6.3).

In the case of a retest (same visit number assigned and same date), the last available measurement for that visit will be used for by-visit summaries. Listings will include scheduled, unscheduled, retest, and early discontinuation data.

Document:

Version Number: 2.0

Version Date: 23APR2024

Template No.: CS\_TP\_BS016 Revision 6

Reference: CS\_WI\_BS005

Effective Date: 02Dec2019

Copyright © 2009, 2010, 2012, 2016, 2018, 2019 [REDACTED]. All rights reserved. The contents of this document are confidential and proprietary to [REDACTED] and its subsidiaries. Unauthorized use, disclosure or reproduction is strictly prohibited.

## 6.5. WINDOWING CONVENTIONS

The on-treatment period for safety assessments will be defined as the period from the day of the first tablet intake up to and including the day of the last tablet intake, extended by 14 days after last tablet.

Windows shown in Table B will be used in the analysis of vital signs and laboratory parameters for analyses performed per visit. Values outside these visit windows, or outside the defined on-treatment period for post-baseline assessments, will be excluded from the analysis of that particular visit. However, no values will be excluded from listings or for the determination of markedly abnormal laboratory (unless outside the defined in-treatment period). If more than one observation is available within a specific visit window, the latest value will be used for analysis.

**Table B Timeframe Used in the per Visit of Vital Signs and Laboratory Parameters**

Definition	Visit	Visit window (treatment day)
Baseline	Visit 1 Screening	<1
On-treatment a	Visit 3 After Cycle 1	29 ± 28 days
	Visit 4 After Cycle 4	113 ± 28 days
	Visit 5 After Cycle 7	197 ± 28 days
	Visit 6 After Cycle 10	281 ± 28 days
	Visit 7 After Cycle 13	379 ± 14 days
	Last measurement	>1

a. From Day 1 until ≤14 days after last tablet intake; Day 1 is defined as day of first study treatment intake.

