Timing				1 st week Cycle 2	3 rd week Cycle 3	1 st week Cycle 5	3 rd week Cycle 6	1 st week Cycle 8	3 rd week Cycle 9	1 st week Cycle 11	3 rd week Cycle 12	1 st day after Cycle 13	14 days after last intake of study drug
Window (days)				+5	+/-3	+5	+/-3	+5	+/-3	+5	+/-3	+3	+5
Gynecological exam	X												X
Breast exam	X												X
PAP test ^c	X												
STI panel ^d	X									X			
Routine laboratory ^e	X												X
Urinalysis	X												X
Pharmacokinetics ^f				X		X							
Adverse events	X	X	X	X	X	X	X	X	X	X	X	X	X

Abbreviations: β -hCG= β -human chorionic gonadotropin; ACOG=American Congress of Obstetricians and Gynecologists; BMI=body mass index; BP=blood pressure; e-Diary=electronic diary; EOS=End of Study; EOT=End of Treatment; ET=Early Termination; HR=heart rate; P=phone contact; PK=pharmacokinetic/s; STI=sexually transmitted infections; V=visit.

- The Screening Visit may be split into 2 separate days if the participant is not able to complete all assessments on the same day. The duration between V1 and V2 should be no less than 7 days and no greater than 42 days.
- The purpose of the phone contact (P1) is to communicate the results of the serum β -hCG test performed at V2 and to reinforce e-Diary instructions.
- Includes medical history regarding illicit drugs, alcohol, and tobacco use.
- Includes pregnancy history and menstrual bleeding history (6 months prior to V1).

- e. Participants will use the e-Diary for at least 1 week during screening to conduct daily assessments of vaginal bleeding/spotting. Participants will receive e-Diary training at V1. Investigators or designees should explain the importance of completing the e-Diary daily. Investigators are to evaluate participant compliance with the e-Diary during screening to assess eligibility. Additional study visits may also be scheduled to provide additional training as needed for participants who continue to fill out the e-Diary incorrectly or incompletely. Participants who are not compliant should be re-trained.
- f. Dispensing only; the first dose will actually be taken at home after Visit 2 (see Section 6.4.1).
- g. See Section 6.4 for information regarding timing of the first dose and management of missed study drug doses.
- h. A negative Visit 2 serum β -hCG test result, to be communicated at P1, in combination with a negative urine home pregnancy test result on the intended day of tablet intake, are both required prior to the first tablet intake.

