8.3.4 Clinical Safety Laboratory Assessments

See [Appendix 3](#) for the list of clinical laboratory tests to be performed and the SoA (Section 1.3) for the timing and frequency.

The Investigator or medically qualified designee (consistent with local requirements) must review the laboratory report, document this review, and record any clinically relevant changes occurring during the study in the AE eCRF. The laboratory reports must be filed with the source documents.

All protocol-required laboratory assessments, as defined in [Appendix 3](#) must be conducted in accordance with the laboratory/procedure manual and the SoA.

If laboratory values from nonprotocol-specified laboratory assessments performed at the institution's local laboratory require a change in study participant management or are considered clinically significant by the Investigator (eg, SAE or AE), then the results must be recorded in the appropriate eCRF.

For any laboratory tests with values considered clinically significantly abnormal during participation up to EOS. Every attempt should be made to perform repeat assessments until the values return to normal or baseline or if a new baseline is established as determined by the Investigator. If such values do not return to normal/baseline within a period of time judged reasonable by the Investigator, the etiology should be identified, and the Sponsor notified.

Screening laboratory safety tests may be repeated once before treatment allocation (V2) at the discretion of the Investigator if the initial results are inconsistent with the participant's clinical

status or recent laboratory results. Screening may be performed between 7 days and 42 days before V2.

Laboratory safety tests (hematology and biochemistry) are scheduled to be repeated at V7 for all participants. If the participant discontinues early from the protocol-specified Treatment Period, those safety tests specified for the EOS Visit (V7) should be completed.

Details on sampling, processing, and shipping of the materials to the central laboratory will be described in a separate laboratory/procedure manual.

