8.4.1 Time Period and Frequency for Collecting AE and SAE Information

All AEs and SAEs will be collected from the signing of the ICF until EOS/ET (Section [1.3](#)).

From the time of signing ICF through EOS/ET(V7), which is 14 to 19 days after last intake of study drug, all AEs, SAEs, and other reportable safety events must be reported by the Investigator. For the analysis of AEs and SAEs, a distinction will be made between:

- **Pre-Treatment AEs:** Events which occur after the ICF (or assent form, if applicable) is signed and before the first intake of study drug.
- **Treatment-emergent AEs:** Events which occur in temporal association with intake of study drug, until 14 days after the last intake of active study drug.

Additionally, any SAE brought to the attention of an Investigator at any time outside the period specified in the previous paragraph must be reported immediately (within 24 hours of learning about the event) to the Sponsor if the event is considered related to study drug.

Investigators are not obligated to actively seek AEs or SAEs or other reportable safety events in former study participants. However, if the Investigator learns of any SAE, including a death, at any time after a participant has been discharged from the study, and he/she considers the event to be reasonably related to the study drug or study participation, the Investigator must promptly notify the Sponsor.

All initial and follow-up AEs, SAEs, and other reportable safety events will be recorded and reported to the Sponsor or designee within the time frames as indicated in [Table 8](#).

The method of recording, evaluating, and assessing causality of AE and SAE and the procedures for completing and transmitting SAE reports are provided in [Appendix 4](#).

Table 8 Reporting Time Periods and Time Frames for Adverse Events and Other Reportable Safety Events

Type of Event	Reporting Time Period: Signing of ICF to First Intake of Study Drug (Day 1)	Reporting Time Period: First Intake of Study Drug (Day 1) through End of Study (V7)	Time Frame to Report Event and Follow-up Information to Sponsor:
Nonserious Adverse Event (NSAE)	Report if: 
• Due to protocol-specified procedure, or• Causes exclusion	Report all	Per eCRF completion guidelines
Serious Adverse Event (SAE)	Report if: 
• Due to protocol-specified procedure, or• Causes exclusion	Report all	Within 24 hours of learning of event

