For continuous measures such as changes from baseline in laboratory tests and vital sign parameters, summary statistics for on-treatment values will be provided in table format at V2 and V7.

For summary statistics of laboratory parameters and vital signs per visit, visit windows as described in [Table 11](#) will be used.

Table 11 Timeframe Used in the Analysis of Vital Signs and Laboratory Parameters

Definition	Visit	Visit window (treatment day)
Baseline	V1 Screening	<1
In-treatment ^a	V3 After Cycle 1	29 \pm 28 days
	V4 After Cycle 4	113 \pm 28 days
	V5 After Cycle 7	197 \pm 28 days
	V6 After Cycle 10	281 \pm 28 days
	V7 After Cycle 13	379 \pm 28 days
	Last measurement	>1

Abbreviation: V=Visit

a. From Day 1 until ≤ 28 days after last tablet intake; Day 1 is defined as day of first study drug intake

Values outside these visit windows, or outside the defined in-treatment period for post-baseline assessments, will be excluded from the analysis of that particular visit.

However, these visit windows will only be applied for analyses performed per visit; no values will be excluded from the determination of markedly abnormal laboratory or vital signs values

(unless outside the defined in-treatment period). If more than one observation is available within a specific visit window, the latest value will be used for analysis.

9.4.3.1 *Adverse Events*

An overview table of the number (percentage) of participants with any AEs, SAE, drug-related AEs, any serious drug-related AEs, any discontinuation due to AE, any discontinuation due to a SAE, any discontinuation due to a drug-related AE, any discontinuation due to serious drug-related AE, and any deaths will be presented for the on-treatment period. Pre-treatment AEs/SAEs starting before the in-treatment period will be excluded from the AE analyses (unless there is an increase in Investigator assessed intensity or causality, or the AE meets SAE criteria post-treatment allocation) and reported in separate frequency tables with the methods described above.

The number (percentage) of participants with at least one AE will be presented in a frequency table of Medical Dictionary for Regulatory Activities (MedDRA) system organ class (according to the primary path) and MedDRA preferred term. The same tables will be presented by relationship to study drug (“Related” and “Not related”) by the Investigator; and by severity of the AE (“mild”, “moderate”, “severe”).

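### SAP Section 3.2 cites Visit 7 timing of 14 days (+5 days) to shorten the laboratory limit, but the limit stops at 14 days, so 5 of 6 permitted days miss the Visit 7 laboratory analysis, if one is tabulated

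*SAP*

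**What the plan says.** Protocol Table 11 (Section 9.4.3) limits post-baseline laboratory and vital sign values as follows: "From Day 1 until ≤ 28 days after last tablet intake". SAP Section 3.2 sets this aside because "the protocol also specifies that the follow-up visit occurs 14 days (+5 days) after the last tablet", and says that the footnote to Table B now corrects it. That footnote reads "From Day 1 until ≤14 days after last tablet intake". SAP Section 6.5 also ends the on-treatment period 14 days after the last tablet.

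Section 6.5 gives the consequence: "Values outside these visit windows, or outside the defined on-treatment period for post-baseline assessments, will be excluded from the analysis of that particular visit". It then adds that "no values will be excluded from listings or for the determination of markedly abnormal laboratory (unless outside the defined in-treatment period").

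The Schedule of Activities (Protocol Section 1.3) times the Visit 7 or early termination (ET) visit "14 days after last intake of study drug", with a window of +5 days and no minus side. Protocol Section 8.4.1 states the range directly: "which is 14 to 19 days after last intake of study drug". On content, Protocol Section 8.3.4 says "Laboratory safety tests (hematology and biochemistry) are scheduled to be repeated at V7 for all participants". The Schedule shows routine laboratory tests and urinalysis only at Visit 1 and at Visit 7/ET.

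**The concern.** The only reason given for the change is when the visit takes place, yet the new limit ends on the first day on which the visit may take place. Because the window is one-sided, any use of the permitted flexibility puts the sample outside the on-treatment period.

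The visit supplies the only scheduled post-baseline hematology, chemistry and urinalysis results, and laboratory abnormality is an endpoint of the primary safety objective in SAP Table A. If a Visit 7 row is produced, its content would depend on whether participants came exactly on day 14 or a few days later. Elsewhere the SAP gives two rules for the same values, so two programmers could both follow it and produce different tables.

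**Working it through.** **Inputs**
- One tablet a day for 13 cycles of 28 days (SAP Section 3.1). Assumption: no gaps or overrun, so the last tablet falls on Day 13 × 28 = 364.
- Visit 7/ET permitted 14 to 19 days after the last tablet (Protocol Sections 1.3 and 8.4.1).
- Limit: last tablet + 14 days (SAP Section 6.5; Table B, footnote a).
- Visit 7 window: Day 379 ± 14 (Table B).

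**Reproducing Table B.** The targets for Visits 3 to 6 equal 28c + 1 for c = 1, 4, 7, 10, which gives 29, 113, 197 and 281. The Visit 7 target is 28 × 13 + 1 + 14 = 379. All match.

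**Permitted days against the limit, for a completer**
- Cut-off: 364 + 14 = Day 378.
- Permitted Visit 7: 364 + 14 to 364 + 19 = Days 378 to 383, six days, all inside the Visit 7 window.
- Kept: Day 378 only, 1 of 6. Excluded: Days 379 to 383, 5 of 6.

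**Table B's own target.** 379 − 364 = 15 days, which is more than 14, so the target fails its own footnote. This holds when the last tablet is on or before Day 364. From Day 365 onward, Day 379 is inside.

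**Visit 7 window.** 379 ± 14 is Days 365 to 393, or 29 days. The 14-day limit keeps Days 365 to 378 (14 days) and cuts Days 379 to 393 (15 days).

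**Alternative limits, same last tablet and same window**

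| Limit after last tablet | Cut-off | Permitted days kept | Window days kept | Day 379 kept |
|---|---|---|---|---|
| 14 days (SAP) | Day 378 | 1 of 6 | 14 of 29 | no |
| 19 days (14 + 5) | Day 383 | 6 of 6 | 19 of 29 | yes |
| 28 days (protocol) | Day 392 | 6 of 6 | 28 of 29 | yes |

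**Who can be affected in the Visit 7 row.** With last tablet on day d, the latest permitted visit is d + 19. It reaches the window only if d + 19 ≥ 365, so d ≥ 346. For earlier discontinuations, the permitted ET days end before the Visit 7 window opens, whatever the limit.

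**Last measurement: two rules.** SAP Section 6.3 defines it as the final value in the study, with no time limit. Section 6.4 points to that definition, and Section 15.3 includes the row in the laboratory summaries. Table B, however, lists Last measurement inside the on-treatment block that carries footnote a. Under that reading a sample taken 15 to 19 days after the last tablet is dropped. The count is again 1 of 6 days kept for any d (permitted d + 14 to d + 19, limit d + 14), for completers and early terminators alike. Protocol Section 9.4.3 did restrict Last measurement to the on-treatment period; SAP Section 3.2 does not list the change of definition.

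**Markedly abnormal values: two rules.** The parenthesis in Section 6.5 removes out-of-period values from the determination. Section 15.3 covers liver values at every visit in the study.

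**The case against.** The strongest reply is that a 14-day period has its own basis. Protocol Section 9.4.3 extends the safety on-treatment period 14 days beyond the last active intake, and SAP Section 15.1 uses 14 days for treatment-emergent adverse events (TEAEs). On this view the limit is sound and only the explanation in Section 3.2 is loose. Consistency with the TEAE period is a fair aim, but Section 3.2 does not give it as the reason. Its reason is visit timing, and the limit does not fit that timing.

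Several limits on the point stand:
- A Visit 7 laboratory row may not exist. One entry in the version 2.0 modification history adds by-visit laboratory tables. Another keeps only baseline and last measurement, but it is cut off, so the output it covers cannot be confirmed.
- The nominal visit, 14 days after the last tablet, is kept.
- The same history removes a markedly abnormal laboratory table and adds a liver listing. If that listing is the only output, no values are lost there.

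A reader might infer that the excluded values disappear from every by-visit laboratory summary. The documents do not support this: under Sections 6.3, 6.4 and 15.3 they enter the Last measurement row, and they are lost there only if Table B's layout overrides Section 6.3. A reader might also infer that early terminators lose values from the Visit 3 to 6 rows. That fails too, because Section 6.4 summarizes only scheduled time points and laboratory tests are not scheduled at those visits.

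**Conclusion.** The point holds as a conflict between SAP Sections 3.2, 6.3, 6.5 and 15.3 and Table B. The 14-day limit contradicts the reason given for it. On a Day 364 last tablet it excludes 5 of 6 permitted days, including Table B's own target, from the Visit 7 laboratory analysis if that row is tabulated. Treatment of the same values under Last measurement and in the markedly abnormal determination is left open by conflicting text.

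The impact is minor. The report is a descriptive safety synopsis of a study that ended early, no testing is done, and Section 15.3 puts all available laboratory data in the listings. Five of six is a count of calendar days. It should not be read as the share of participants lost, because the documents do not say on which days visits took place or how many participants reached Visit 7. The Day 379 statement requires a last tablet on or before Day 364, and the Visit 7 row can be affected only for a last tablet on Day 346 or later.

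**What to change.** For laboratory data, change the limit in SAP Section 6.5 and Table B footnote a to 19 days after the last tablet (14 + 5), or state that any Visit 7/ET value counts. State that Last measurement follows Section 6.3, record that change of definition in Section 3.2, and state that the markedly abnormal liver determination follows Section 15.3. Leave the TEAE and pregnancy rules unchanged.

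The cost is one constant in the programs, wording in a few sections and Table B, and one table footnote. The downside is that laboratory values from days 15 to 19 after the last tablet would count as on-treatment, while adverse events starting on those days remain post-treatment. The table footnote should say so.
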